# Safety Endpoints

### Adverse Event Monitoring Questionnaire (At 1, 3, and 6-months)

Vestibular Stimulation to Trigger Adipe Clinical Trial Project Name	70 of 112		
Clinical Protocol for VeS			
243973(NI)_181094(UCSD USA) Study Reference Number		01 Document Number	11 Revision Number

Based on the survey of adverse events devised by Utz et al. (2011) occurrence of the following adverse events will be specifically enquired about by having the subjects complete the Adverse Event questionnaire: headache; pain/irritation behind the ears; vertigo/ dizziness; blurred vision; nausea; fatigue/ tiredness; seizures; tinnitus; and other symptoms. This will be done in person during the 3 and 6 months in person and at the 1-month timepoint, this questionnaire will be conducted via telephone or by email. It will also be completed on an ad hoc basis should the need arise. The questionnaire will ascertain if any of these symptoms occur during or after use of the device, and if so how frequently.

We will monitor each instance of an adverse event causing a dropout from the study. The dropouts, together with causes, will be recorded and reviewed at the end of the study. This guidance from the FDA will be followed: https://www.fda.gov/downloads/RegulatoryInformation/Guidances/UCM126572.pdf. If it becomes evident that the proportion of subjects who drop out due to safety concerns/ adverse events convincingly exceeds 30%, the study will be halted.

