# 24.3 Independent Data Monitoring Committee (DMC)

There are no safety issues with the device that require a DMC for safety monitoring in this study.

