# 27. Causality and Severity Assessment of Adverse Events

The investigator-sponsor will promptly review documented adverse events and abnormal laboratory results to determine 1) if the abnormal laboratory finding should be classified as an adverse event; 2) if there is a reasonable possibility that the adverse event was caused by the investigational medical device or, if applicable, other study treatment or diagnostic product(s); and 3) if the adverse event meets the criteria for a serious adverse event.

If the final determination of causality is unknown and of questionable relationship to the investigation medical device or, if applicable, other study treatment or diagnostic products(s), the adverse event will be classified as associated with the use of the investigation medical device or, if applicable, other study treatment or diagnostic products(s) for reporting purposes. If the final determination of causality is unknown but not related to the investigational medical device or, if applicable, other study treatment or diagnostic products(s), this determination and the rationale for the determination will be documented in the respective subject's case report form.

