## 32. Suspension, Termination and Close-Out of Clinical Investigation

## 32.1 Suspension or Premature Termination of Clinical Investigation

Reasons for suspension or premature termination at an investigation site may include incidences where monitoring or auditing identifies serious or repeated deviations on the part of an investigator. The FDA and IRB will be notified of any suspension or early termination of the clinical investigation, together with all other principal investigators, in the event that the suspension or termination was due to safety issues. A principal investigator may suspend or prematurely terminate participation in the clinical investigation at the investigation sites for which they are responsible.

If suspicion of an unacceptable risk to subjects arises during the clinical investigation, or when so instructed by the IRB or regulatory authorities, the clinical investigation will be suspended while the risk is assessed. The clinical investigation will be terminated if an unacceptable risk is confirmed. Should the risk not be confirmed justification and data supporting the decision to resume the clinical investigation will be provided to the relevant persons.

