#### Interim Analysis

There is no planned interim analysis.

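### The 30% adverse-event dropout stop has no assigned in-study tally, denominator or evidence standard, and the only timed collated review of dropouts comes at the end of the study

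*Protocol*

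**What the plan says.** One paragraph of the protocol's safety endpoints (Section 18.3, under the adverse event questionnaire) makes three statements:

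- On single cases: "We will monitor each instance of an adverse event causing a dropout from the study".
- On the collected cases: "The dropouts, together with causes, will be recorded and reviewed at the end of the study".
- On stopping, once it becomes clear that "the proportion of subjects who drop out due to safety concerns/ adverse events convincingly exceeds 30%, the study will be halted".

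On oversight, Section 24.3 says "There are no safety issues with the device that require a DMC for safety monitoring in this study". Section 34.1 says "There is no planned interim analysis", and Section 36.1 repeats it.

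Other protocol sections act while the trial is running:

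- Section 20.6 has every discontinuation documented with its reason.
- Section 27: "The investigator-sponsor will promptly review documented adverse events and abnormal laboratory results".
- Section 31 sends a dropout's data to the assigned statistician when that participant leaves.
- Section 32.1 says that on suspicion of unacceptable risk "the clinical investigation will be suspended while the risk is assessed".

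The SAP adds no in-study rule. Its Section 11.1 reports discontinuations due to adverse events in the disposition summary, which belongs to the final analysis after lock and unblinding (SAP Section 4).

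**The concern.** A halt has a purpose only while participants are still using the device. The stopping criterion is a cumulative proportion, so someone has to add up cases and divide. The only such review with a stated time falls after the last participant has finished, and no sentence in either document gives the sum to anyone earlier. With four sites, no single site sees the overall figure.

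Four things needed to apply the rule are absent: who computes the proportion, how often, on which denominator (all participants or one arm), and what *convincingly* requires. The denominator matters most. Site staff are blinded, so a count they could make for themselves would be pooled, and pooling dilutes an excess that is confined to the active arm.

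This is the only numerical safety stop in either document, and a reader of the protocol would take it as a working protection. The expected device effects in Section 16.1 are skin irritation, disequilibrium, nausea, vomiting and headache. If non-serious, dropouts for these would not pass through the expedited reporting routes. The dropout rule is the safeguard aimed at them.

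**Working it through.** **Inputs.** The threshold is 30% (Section 18.3). Recruitment is 200, from 180 evaluable and 10% anticipated dropout (Section 34.3, Power Calculation). Allocation is 1:1, so 100 per arm is assumed. Sham adverse-event dropout is not given; 0%, 5% and 10% are assumed as a range.

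**The plan's own figure.** 180 / (1 − 0.10) = 200, which reproduces the stated recruitment. The 30% has no derivation in the documents, so there is nothing to reproduce for it.

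**Pooled or per arm.**

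- Thirty active-arm dropouts are 30/100 = 30% of that arm. With none on sham they are 30/200 = 15% pooled.
- Pooled proportion = (100 × p_active + 100 × p_sham) / 200. Setting this to 0.30 gives p_active = 0.60 − p_sham.

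| Sham adverse-event dropout (assumed) | Active-arm dropout when pooled is 30% |
|---|---|
| 0% | 60% |
| 5% | 55% |
| 10% | 50% |

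Sixty of 200 is exactly 30%, so the pooled figure is first exceeded at 61.

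**The evidence standard.** One possible meaning of *convincingly* is that an exact (Clopper–Pearson) one-sided lower limit lies above 30%. That is my assumption, made only to show the spread. The limit for x of n is the α quantile of Beta(x, n − x + 1), and the table gives the smallest x that passes.

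| Denominator | Point estimate above 30% | 95% lower limit above 30% | 97.5% lower limit above 30% |
|---|---|---|---|
| 200 pooled | 61 | 72 | 74 |
| 100 in one arm | 31 | 39 | 40 |

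The undefined wording therefore leaves the trigger anywhere from 31 participants in one arm to 74 overall.

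**Timing, as illustration only.** Suppose the count were examined after every 20 participants with the 97.5% limit, each outcome being known at the look. In 20,000 simulated trials with a true dropout rate of 50%, about 99% would have halted by 100 participants, at a median of 40. With a true rate of exactly 30%, about 7% would halt at some look. Real follow-up is staggered, so actual exposure would be higher than this. A review at the end would find the same excess after all 200 had been exposed.

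**In-study provisions against what the rule needs.**

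| Provision | What it supplies | Does it yield the proportion? |
|---|---|---|
| 18.3, monitoring of each case | Awareness of single dropouts | No |
| 20.6, documented reasons | The numerator's raw data | Not tallied during the trial; the withdrawal list gets its allocations only after unblinding |
| 27, prompt event review | Causality and seriousness of each event | No |
| 31, data sent at dropout | Data reaching a statistician | Could, but no tally is assigned |
| 32.1, suspension | A power to stop | Does not mention the 30% rule |

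**The case against.** The strongest reply is that the paragraph is coherent: each adverse-event dropout is followed as it occurs, the trial halts if an excess becomes evident, and the causes are gathered in a tidy review afterwards. Much of that stands. A reader might infer that the stop cannot operate at all, that dropouts are looked at only at the end, or that the rule could never protect a participant. The documents do not support those readings. Section 18.3 commits to following each case, and Sections 20.6, 27, 31 and 32.1 let information accumulate and allow suspension while the trial runs.

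Nor does the absence of a monitoring committee or an interim analysis disable the rule. The sponsor could apply it, a running count is not an interim analysis, and going without a committee is a reasoned choice for a device the protocol classes as non-significant risk.

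Blinding is also a smaller obstacle than it seems. Section 24.2 sends the master code to statisticians who have no contact with participants, so a per-arm count is feasible, though no one is asked to make it.

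The scenario is remote under the plan's own assumption. At 10% all-cause dropout the chance of 61 or more among 200 is below 10⁻¹⁴. But a safety stop is there for the case where that assumption is wrong.

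The paragraph also says that an FDA guidance will be followed. I cannot see that document and rely on it for neither side.

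What the reply does not meet is that these provisions work on single events or single participants, while the rule works on a proportion that nobody is told to compute.

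**Conclusion.** The point holds as an unfinished rule with a conflict of timing. The protocol states a halt on a cumulative proportion, gives the end of the study as the only time for collated review, and assigns no tally before then. A halt remains possible through event-level oversight, but it would depend on someone noticing rather than on a procedure.

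The size lies in the ambiguity. If the count is pooled, the active arm could reach 50% to 60% adverse-event dropout before the pooled figure reaches 30%. That range rests on 100 per arm and an assumed sham rate of 10% down to 0%. The spread of 61 to 74 pooled dropouts rests on my assumed readings of the evidence standard. Nothing here bears on whether 30% is the right value. The change should be made, because a stated safeguard is undercut by a stated timing and the remedy is cheap.

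**What to change.** Reconcile the sentences in Section 18.3 so that the cumulative adverse-event dropout proportion is tallied and reviewed while the trial can still be halted. The text should state:

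- which role, outside the blinded site team, keeps the count across all four sites, and how often. The statisticians who hold the code under Section 24.2 are one option. SAP Section 6.2 has the lead statistician request the randomization list alongside the locked data, so if that person is to stay blinded until lock, name someone else;
- whether the percentage is per arm or pooled, and whether its denominator is everyone randomized or those enrolled so far;
- what evidence counts as convincing, and to whom the result goes, with a cross-reference to Section 32.1.

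The end-of-study summary of causes can stay as an addition. The threshold and its clinical meaning remain with the sponsor's clinicians. The cost is protocol wording, the approval this needs, and a running count of data already recorded under Sections 20.6 and 31. It requires no monitoring committee, efficacy look or change in sample size.

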# **19. Number of Subjects and Investigational Sites**

An anticipated number of 200 patients shall participate in the device investigation. Subject enrollment will take place across two sites:

- 1. University of California San Diego (UCSD)
- 2. University of Ulster (UU)
- 3. Texas Diabetes and Endocrinology (TDE) site

# 20. Subject Selection

20.1 *Target Population* 

Patients who are overweight.

20.2 Subject Selection

# Pre-enrollment Screening

Prior to being allowed to start the study proper, potential subjects with type 2 diabetes should be excluded by means of a fasting blood glucose test. This can be via a finger prick sample and glucose meter. Testing should

Vestibular Stimulation to Trigger Adip Clinical Trial Project Name	71 of 112		
Clinical Protocol for VeS			
243973(NI)_181094(UCSD USA) Study Reference Number	Protocol Document Type	01 Document Number	11 Revision Number

be done in the morning after an overnight fast of at least 8 hours. If the reading is 126 mg/dl or above, then the potential subject will be excluded from the study and asked to see their primary care physician in order to be investigated for type 2 diabetes mellitus. At the same Screen Visit subjects will complete a questionnaire about their medical history and medications to ensure that they fulfil the inclusion and exclusion criteria for the study. Any concomitant medications taken by the subject will be captured via the Concomitant Medication Form. The questionnaire will be identified using an alphanumeric code and will not have any identifiable subject data on them. The source documents will be securely stored at the Clinical Site.

The following procedures will also be performed during the Screening process:

- Obtain Informed Consent
- Obtain demographic data, including gender, date of birth/age, race, and ethnicity;
- Screening questionniare to confirm conformity with inclusion and exclusion criteria access to medical records not required, medical history collected via questionnaire.
- Measurement of height and weight to allow BMI to be calculated
- Pregnancy test on urine (for women of childbearing potential only)
- Hypothyroidism screening test
- Fingerprick blood glucose

# 20.3 Subject Recruitment

The clinical sites at UCSD) will recruit subjects via Research Match (see:

https://actri.ucsd.edu/clinical/Pages/using-ResearchMatch.aspx). This is a "is a NIH-sponsored national registry of volunteers who have indicated a willingness to learn more about research studies." The aim of this registry is to connect "researchers with appropriate potential subjects." The UCSD and TDE sites will also recruit via social media advertizing (e.g. Facebook), social networking advertizing (e.g. Craigslist), newspaper adverts, posters, leaflets, tabling events, use of volunteer databases and potentially radio advertizing.

For the TDE site, as they are a clinical practice with an internal research centre, they will also recruit subjects via their patient database. Existing patients may be called or sent emails with the relevant study information or through social media or network advetrtising as well.

Vestibular Stimulation to Trigger Adip Clinical Trial Project Name	72 of 112		
Clinical Protocol for VeS			
243973(NI)_181094(UCSD USA) Study Reference Number		01	11 Revision Number

For the clinical trial site based in Northern Ireland potential subjects will be targeted via social media campaigns such as Facebook, Twitter and Instagram as well as radio and local news advertising.

In order to improve recruitment numbers, we also plan to post recruitment flyers in the hospitals and universities associated to where the clinical trial is taking place. The advertisement to Facebook groups relating to weight loss that operate in the local areas where the clinical sites are located; if necessary Neurovalens may ask Facebook to promote this statement via a paid advertisement.

Neurovalens shall be responsible for recruitment and shall follow best practice for the management of bias in subject recruitment.

## 20.4 Inclusion Criteria

- 1. Signed informed consent
- 2. Body mass index BMI  $\ge$  27 kg/m2.
- 3. Males or Females. Note females of child-bearing potential must have a negative urine pregnancy test at screen and also just before each DXA scan. (As DXA involves a small dose of ionizing radiation). They should agree to follow a physician-approved contraceptive regimen for the duration of the study period (other than DMPA injections as this causes weight gain).
- 4. 22-80 years of age inclusive on starting the study. (In order to comply with FDA guidance: https://www.fda.gov/MedicalDevices/DeviceRegulationandGuidance/GuidanceDocuments/ucm08974 0.htm#s6)
- 5. Ability and willingness to complete all study visits and procedures; in particular an agreement to engage with: trying to use the device on a daily basis; the hypocaloric diet weight loss program; and this provided weight loss support and mentoring.
- 6. Agreement not to use of prescription, or over-the-counter, weight loss preparations for the duration of the trial.
- 7. Agreement not to start smoking tobacco or marijuana for the duration of the study.
- 8. Access to Wi-Fi (to connect iPod to internet)

## 20.5 Exclusion Criteria

- 1. History of vestibular dysfunction or other inner ear disease as indicated by the screening questions.
- 2. History of bariatric surgery, or gastric resection.

Vestibular Stimulation to Trigger Adip Clinical Trial Project Name	73 of 112		
Clinical Protocol for VeS	TAL		
243973(NI)_181094(UCSD USA) Study Reference Number		01	11 Revision Number

- 3. History of skin breakdown, eczema or other dermatological condition (e.g. psoriasis) affecting the skin behind the ears.
- 4. History of weight loss device implantation (e.g. VBloc Maestro or Abiliti).
- 5. Use of a non-invasive weight loss device (e.g. Modius)
- 6. Hypothyroidism requiring current treatment with levothyroxine (e.g. Levo-T, Synthroid, Thyroxine) (Other thyroid disorder patients on stable treatment for at least 3 months are acceptable).
- 7. Other endocrinological causes of weight gain (e.g. Cushing's disease, Cushing's syndrome or acromegaly)
- 8. Previous diagnosis of HIV infection or AIDS (HIV is known to cause a vestibular neuropathy which would prevent VeNS from working).
- 9. Diagnosis of cirrhosis, chronic pancreatitis, or liver, kidney or heart failure.
- 10. Treatment with prescription weight-loss drug therapy in the 6 months before starting the study.
- 11. Tobacco smoking (including vaping) in the six months prior to starting and for the duration of the study.
- 12. Use of marijuana (smoking, vaping or in edible form) more than twice a month on average.
- 13. Known genetic cause of obesity (e.g., Prader-Willi Syndrome).
- 14. Body weight change of more than 20% in either direction within the previous year.
- 15. Physician-prescribed diet, and/ or current, active member of an organized weight loss program.
- 16. Diabetes mellitus (Types 1 & 2).
- 17. Diagnosis of epilepsy or use of anti-epileptic medication within six months of starting the study (e.g. for the treatment of peripheral neuropathy)
- 18. Chronic (more than a month of daily use) treatment with opioid analgesic drugs within the last 6 months.
- 19. Regular use (more than twice a month) of anti-histamine medication within the last 6 months.
- 20. Use of oral or intravenous corticosteroid medication within 6 months of starting the study.
- 21. Use of the beta-blockers atenolol, metoprolol or propranolol within 3 months of starting the study.
- 22. Current alterations in treatment regimens of anti-depressant medication for whatever reason (including tricyclic antidepressants) (Note: stable treatment regimen for prior 6 months acceptable).
- 23. An active diagnosis of cancer.
- 24. A myocardial infarction within the preceding year.
- 25. A history of stroke or severe head injury (as defined by a head injury that required craniotomy or endotracheal intubation). (In case this damaged the neurological pathways involved in vestibular stimulation).
- 26. Presence of permanently implanted battery powered medical device or stimulator (e.g., pacemaker, implanted defibrillator, deep brain stimulator, vagal nerve stimulator etc.).

Vestibular Stimulation to Trigger Adip Clinical Trial Project Name	74 of 112		
Clinical Protocol for VeS			
243973(NI)_181094(UCSD USA) Study Reference Number	Protocol	01 Document Number	11 Revision Number

- 27. Psychiatric disorders (including untreated severe depression, schizophrenia, substance abuse, eating disorder etc.)
- 28. Current participant in another weight loss study or other clinical trial.
- 29. Have a family member who is currently participating or is planning to participate in this study.
- 30. Weight over 350 pounds at UU, TDE and CTRI site (as this is the weight limit of the DXA scanner) or a weight over 500 pounds at the EPARC site (as this is the weight limit of the DXA scanner)
- 31. Pregnancy

The decision to exclude participants with type 2 diabetes mellitus was made after reading the FDA's draft guidance (see: http://www.fda.gov/downloads/Drugs/.../Guidances/ucm071612.pdf). This notes that, "[c]compared with nondiabetic patients, overweight and obese patients with type 2 diabetes often respond less favorably to weight-management products and may face unique safety issues such as risk for sulfonylurea-induced hypoglycemia following weight loss (if the dose of sulfonylurea is not appropriately lowered or the drug discontinued)."

The FDA then go on to advise "examining the efficacy and safety of weight-management products in trials dedicated to patients with type 2 diabetes." On the basis of this advice we made the decision to exclude patients with type 2 diabetes. This is an important patient group of course, and our intention is to investigate type 2 diabetics in due course.

If a subject is found to possibly have type 2 diabetes during the initial screening, then they will be excluded and asked to notify their primary care physician. However, if a subject passes the initial screening but a suspicion of this diagnosis arises during one of the study tests, then the subject will be asked to notify their primary care physician, though they will still be allowed to complete the study.

# 20.6 Withdrawal criteria

These processes are to be implemented at both study sites.

Subjects who do not meet the screening criteria will be considered screen failures and will be replaced.

Vestibular Stimulation to Trigger Adip Clinical Trial Project Name	75 of 112		
Clinical Protocol for VeS			
Document Title			
243973(NI)_181094(UCSD USA)	Protocol	01	11
Study Reference Number	Document Type	Document Number	Revision Number

Subjects may withdraw from the investigation for any reason, at any time. Subjects are free to participate or not participate as they wish.

During the course of the study, subjects may be withdrawn from further involvement. Reasons for withdrawal may include:

- Subject removal of consent
- Any adverse event (related or not) that in the opinion of the investigator will endanger the well-being of the subject if they continued in the study.
- Poor compliance with the study requirements (protocol violation)
- Subjects lost to follow-up

All subjects withdrawn from the study due to unexpected device effect, directly related to the clinical investigation, will be followed-up and treated until the effect resolves.

Subjects who are withdrawn will not be replaced. All discontinuations will be documented along with the reason for withdrawal. Reasonable efforts will be made to contact any subject lost to follow-up during the course of the investigation in order to complete assessments and retrieve data. Should a subject be lost to follow-up the data available will be used in the final report, all uses of partial data will be documented. Ethics Committees and regulatory authorities will be notified of withdrawal as required by the regulations.

If possible, when a subject withdraws, or is withdrawn, a final visit should be conducted to allow a withdrawal discussion with the subject. At this visit the study device, iPod and any unused consumables should be collected. Also, at this visit it will be requested in a non-coercive manner if the subject will permit their weight to be taken, and if they are willing to complete the Adverse Event monitoring questionnaire. Moreover, if the subject had reached the point where they were due a follow-up appointment (i.e. at 3 and 6 months), then they be asked, again in a non-coercive manner, whether they are willing to have the scheduled tests and measurements for that appointment. It will though be made clear to the subject that these activities are optional on their part.

If the subject does not wish to return for a final visit, then a withdrawal discussion on the telephone will be attempted. In this discussion factual information may be provided to the subject and arrangements made for end-of-study activities like return of study investigational device, payment of any outstanding compensation

Vestibular Stimulation to Trigger Adip Clinical Trial Project Name	76 of 112		
Clinical Protocol for VeS			
243973(NI)_181094(UCSD USA) Study Reference Number		01	11 Revision Number

and whether the subject will complete the adverse event questionnaire over the phone. There will be no attempt to coerce or unduly influence the subject.

A list will be assembled of all subjects who withdrew, or were withdrawn, from the study after enrollment. This will be broken down by center and treatment group and contain the following information: subject ID; specific reason for discontinuation; duration of treatment and last day of study adherence before discontinuation; whether or not the blind for the subject was broken at the time of discontinuation; if the subject returned the study device; and, after conclusion of the study and unblinding, what that subject's treatment allocation was – i.e. active device or sham.

